4.5 Subject Withdrawal/Discontinuation Criteria

In this study, pembrolizumab administration will continue until one of the following conditions is observed.

4.5.1. Disease progression [RECIST Criteria 1.1.]

Disease progression is defined as rapid growth of multiple measurable or non-measurable lesions. (Note: the appearance of one or more new lesions is also considered progression).

4.5.2 Noncompliance:

If the patient is not able to remain compliant with the treatment schedule in the absence of toxicity, the study treatment should be discontinued for the patient.

4.5.3. Sustained side effects:

Study treatment will be discontinued for patients who have sustained toxic effects that are attributed to the study drug and require a dose interruption lasting more than 12 weeks.

4.5.4. Initiation of new anticancer treatment:

In patients for whom the investigator, in his or her judgment, determines new treatment for breast cancer is warranted, the study treatment may be discontinued.

4.5.5. Patient withdraws consent.

In the event that a patient withdraws consent, the reason(s) for withdrawal must be documented. Patients must be informed that their participation in the study is voluntary and that they may choose not to take part in the study or to stop taking part at any time. If a patient chooses not to take part in the study or to stop at any time, his/her future medical care or medical benefits will not be affected.

4.5.6. Patient has completed 24 months of treatment. However, if the patient remains progression free, she/he will continue the hormonal blockade therapy to complete a total of 5 years to 10 years based on the risk stratification and the discretion of the physician. Patient will be taken off-study after completion of Pembrolizumab.

4.6 Criteria for Disease Control

The purpose of this study is to maintain progression free status by additional immune modulation with pembrolizumab to enhance the surveillance and suppression of tumor that is currently done only by hormone receptor blocking agents.

4.6.1. Response will not be considered evaluable in the following categories:

4.6.1.1. Early Deaths: Patients who die within the first 2 weeks of the initiation of drug therapy owing to concurrent disease. These cases will be considered treatment failures in the intent-to-treat analysis.

4.6.1.2. Lost to Follow-up: Patients for whom there is inadequate information to judge tumor response because of loss of contact with our institution (>2 months after a missed appointment) and with referring physician in spite of repeated attempts to locate them. These cases will be considered treatment failures in the intent-to-treat analysis.

4.6.1.3. Major Protocol Violation: Patients who significantly deviate from the treatment program by either adding or deleting another agent or another therapeutic maneuver or by modifying schedule substantially (delay treatment ≥ 7 days without administration reason) of the drug under evaluation. Patients who do not fulfill the requirements outlined under Patient Eligibility are also included in this category. Patients on the concurrent radiation arm due to excess toxicity who do not complete the planned radiation will not be considered violations if they continue systemic therapy per protocol plan

5.0 STUDY FLOW CHART

Trial Period:	Screening Phase	Treatment Cycles								End of Treatment ^h	Post-Treatment		
		1	2	3	4	8 cycles and beyond					If patient returns to clinic	Safety follow up ^f	Follow Up ^g
Treatment Cycle/Title:	Screening /Baseline												
Scheduling Window (Days):			± 3	± 3	± 3	± 3	± 3	± 3	± 3			1 month after last dose	24 months
Informed Consent	x												
Inclusion/Exclusion Criteria	x												
Demographics and Breast Cancer History ^a	x												
Concomitant Medication Review per SOC	x												
Physical Exam ^b , V/S	x	x	x	x	x	x	x	x	x	x			
Adverse Events ^b	x	x	x	x	x	x	x	x	x	x	x	x	
ECOG Performance Status ^b	x	x	x	x	x	x	x	x	x	x			
Pregnancy Test – Urine or Serum β-HCG (for women with childbearing potential)	x												
CBC and Biochemical Profiles ^c	x	x	x	x	x	x	x	x	x	x			
TSH, Free T4 and Total cortisol ⁱ	x			x		x		x		x			
Radiological Evaluation as clinically indicated and as SOC ^d	x									x			
Archived biopsy and/or surgical specimens (block or unstained slides) obtained at any time prior to treatment.	x												
Correlative Studies Blood Collection ^e	x				x			x		x			
Optional tumor sample collection at disease progression, if the site is accessible										x			
Disease Progression Status												x	
Pembrolizumab Administration		x	x	x	x	x	x	x	x				
Hormonal Therapy		x	x	x	x	x	x	x	x				
Radiation Therapy ^j		x	x										

- a. Demographics include patient's age, gender and race. Medical history includes primary breast cancer pathological diagnosis, ER/PR/HER2 status. Prior therapies and procedures for breast cancer,
- b. Complete physical exam, ECOG performance status and adverse events assessment during the screening period will not be repeated if done within 30 (+/- 3 days) days before the start of treatment. Physical exam will be performed every 2nd cycle throughout the study unless the patient is having side effects that require more frequent monitoring. Adverse events will be collected each cycle – on cycles when a physician follow-up is not scheduled, the study coordinator will meet with the patient to review these. For patients who are receiving concurrent radiation with study treatment, adverse events will be monitored on a weekly basis during the radiation therapy period.
- c. Hematologic and biochemical profiles (CBC, albumin, alkaline phosphatase, ALT, AST, LDH, uric acid, calcium, glucose, phosphorus, potassium, sodium, magnesium, total bilirubin, total protein, BUN, as standard of care (will not be repeated if done within 30 (+/- 3 days) days before the start of treatment). During treatment, an earlier evaluation will be performed if clinically indicated.
- d. Radiological evaluation may include CT of the chest, and/or abdomen, and/or pelvis, ultrasound, bone scan and X-Rays as clinically indicated for standard of care. PET/CT, chest wall/breast photos, EKG and ECHO or MUGA may also be performed as indicated for standard of care. If follow up evaluations are necessary, the same method of evaluation, specific to the subject's condition, will be performed as clinically indicated. Patients without symptoms of recurrent or cardiac toxicity will not receive imaging per national guidelines.
- e. Peripheral blood and serum for correlative studies. Approximately 50 cc of blood will be drawn at baseline, and after every 3 cycles (i.e. after 3rd, 6th, 9th, 12th, etc) and at disease progression (if applicable). Patients who remain on study for all 34 cycles will not have the last sample drawn before cycle 34. The last blood collection for these patients who complete all 34 cycles of study treatment will be at the end of study visit after the 34th cycle of Pembrolizumab
- f. The mandatory Safety Follow-Up Visit should be conducted approximately 30 days after the last dose of trial treatment or before the initiation of a new anti-cancer treatment, whichever comes first. All AEs that occur prior to the Safety Follow-Up Visit should be recorded. Safety Follow-Up Visit can be done in the clinic, or by phone if patient is not willing to come to the clinic for follow up.
- g. Disease progression status follow up: 24 months after the first treatment of the study regimen for patients who were taken off study treatment for reasons other than disease progression.
- h. The end of 24 months of treatment or until meet drug discontinuation criteria, whichever occurs first.
- i. TSH, Free T4 and Total cortisol level will be monitored at baseline, then every 2 cycles and at disease progression as standard of care.
- j. Patients may begin Pembrolizumab and endocrine therapy concurrently with radiation or after radiation based on physician discretion. For patients receiving concurrent radiation and study treatment, radiation will begin 7 days (+/- 3 days) prior to administration of pembrolizumab and initiation of endocrine therapy. Concurrent pembrolizumab and radiation is not required.

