4.1.2 Exclusion Criteria

1. Is currently participating in a study of an investigational anti-cancer agent.
2. Has a diagnosis of immunodeficiency or any other form of immunosuppressive therapy.
3. Has not recovered from adverse events due to prior therapies, i.e. monoclonal antibody, chemotherapy, targeted small molecule therapy, radiation therapy, or surgery.
 - Note: Subjects with \leq Grade 2 neuropathy, alopecia and general disorders and administration site conditions (per CTCAE version 4.0) are an exception to this criterion and may qualify for the study.
4. Has a known history of prior malignancy with the exception of basal cell carcinoma of the skin, superficial bladder cancer, squamous cell carcinoma of the skin, or in situ cervical cancer, and has undergone potentially curative therapy and has no evidence of recurrence over the last 1 year since completion of curative therapy.

5. Has an active autoimmune disease requiring systemic treatment within the past 3 months or a documented history of clinically severe autoimmune disease, or immunosuppressive agents. Subjects with vitiligo or resolved childhood asthma/atopy would be an exception to this rule. Subjects that require intermittent use of bronchodilators, inhaled steroid or local steroid injections to the skin would not be excluded from the study. Subjects with hypothyroidism stable on hormone replacement or Sjögren's syndrome will not be excluded from the study.
6. Has a history of (non-infectious) pneumonitis that required steroids or current pneumonitis.
7. Has an active infection requiring systemic therapy.
8. Has known psychiatric or substance abuse disorders that would interfere with cooperation with the requirements of the trial.
9. Has received prior therapy with an anti-PD-1, anti-PD-L1, anti-PD-L2, anti-CD137, or anti-Cytotoxic T-lymphocyte-associated antigen-4 (CTLA-4) antibody (including ipilimumab or any other antibody or drug specifically targeting T-cell co-stimulation or checkpoint pathways).
10. Has a known history of Human Immunodeficiency Virus (HIV).
11. Has a known active Hepatitis B or Hepatitis C
12. Have received a live vaccine within 30 days prior to the first dose of trial treatment.
13. Gastrointestinal tract disease or defect or previous history of colitis.
14. Has proven or suspected distant metastasis that involves occurrence of breast cancer outside of loco-regional breast and lymph nodes area.

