- Unless otherwise noted, the electronic SAE application (eSAE) will be utilized for safety reporting to the IND Office and MDACC IRB.
- Serious adverse events will be captured from the time of the first protocol-specific intervention, until 30 days after the last dose of drug, unless the participant withdraws consent. Serious adverse events must be followed until clinical recovery is complete and laboratory tests have returned to baseline, progression of the event has stabilized, or there has been acceptable resolution of the event.
- Additionally, any serious adverse events that occur after the 30 day time period that are related to the study treatment must be reported to the IND Office. This may include the development of a secondary malignancy.
- Notable events must be recorded in the eSAE program in order to be submitted to sponsor. Reporting of notable events is the responsibility of the investigator.

7.6.2 Reporting to FDA:

- Serious adverse events will be forwarded to FDA by the IND Sponsor (Safety Project Manager IND Office) according to 21 CFR 312.32.

It is the responsibility of the PI and the research team to ensure serious adverse events are reported according to the Code of Federal Regulations, Good Clinical Practices, the protocol guidelines, the sponsor's guidelines, and Institutional Review Board policy.

7.6.3 Investigator Communication with Supporting Companies:

The MDACC Internal SAE Report Form will be used for reporting to Merck Global Safety ([contact]).

Reporting Timeline:

- Deaths that is unanticipated and definitely, probably or possibly related to study intervention that occur during and within 30 days after the last day of active study intervention will be reported to Merck within 24 working hours.
- All other SAEs that are serious, unanticipated, and definitely, probably or possibly related to study drugs will be reported to Merck within 2 working days.

Non-serious Events of Clinical Interest will be forwarded to Merck Global Safety and will be handled in the same manner as SAEs.

Immediate Reporting of Adverse Events to Merck:

Serious Adverse Events

A serious adverse event is any adverse event occurring at any dose or during any use of Merck's product that:

- Results in death;
- Is life threatening;
- Results in persistent or significant disability/incapacity;
- Results in or prolongs an existing inpatient hospitalization;
- Is a congenital anomaly/birth defect;
- Is another important medical event

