0.50	24.0	0.775	19.0
0.60	18.2	0.947	13.7

Safety Run-in

At any time within first 6 patients are treated, if ≥ 2 patients experience serious adverse events (SAE) within first 3 cycles of treatment, we will stop the trial and claim that the regimen is too toxic. An SAE is defined as an adverse event that is serious, unexpected, and related to the study drug. This study will be monitored by the IND Office. During the safety run-in and throughout the study, patients who have completed 3 cycles of treatment will be considered as evaluable for safety and response.

Analysis of Primary and Secondary Endpoints

The primary endpoint of DFS will be summarized at 2 years with a corresponding 95% confidence interval. DFS will be compared with the historical control rate of 60% at year two by using a one-sided exponential MLE test. Cox proportional hazards regression analysis will be used to model the association between DFS and disease and demographic covariates of interest, including immune-related biomarkers in the peripheral blood and tumor tissue. Overall survival (OS) from the start of the study will be analyzed similarly to DFS. Adverse events will be summarized by grade and category.

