10.0 DATA MANAGEMENT

The Principal Investigator is responsible for assuring that the data entered into the database are complete and accurate and that data entry is performed in a timely manner.

10.1 Data collection for this study including:

- 1) demographic information (sex, race, and date of birth),
- 2) date of initial breast cancer diagnosis, pathology report of primary breast cancer, biomarker status, and date and location of distant metastases at disease progression;
- 3) history of breast cancer surgery, and radiation therapy, if applicable; radiation therapy timing with respect to initiation of pembrolizumab
- 4) date and type of chemotherapy and/or hormonal therapy for metastatic disease;
- 5) All AEs will be collected, however only $>/=2$ non-hematologic AEs and $>/=3$ hematological AEs will be recorded. Other abnormal laboratory values will not be reported as AEs; however, any clinical consequences of abnormality should be reported as AEs.
- 6) Concomitant medication will be recorded per standard of care in the electronic medical record, and will not be recorded in the study database.
- 7) All data collected for this study will be shared with Baylor College of Medicine ([name]) with compliance of data confidentiality plan.

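### Overall survival is to be analysed, but patients who stop for progression have no scheduled survival follow-up and no OS censoring rule is given

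*Combined protocol and SAP*

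**What the plan says.** The OS commitment is one sentence in section 8.0, under the analysis of primary and secondary endpoints: "Overall survival (OS) from the start of the study will be analyzed similarly to DFS". The same paragraph summarises DFS at 2 years with a 95% confidence interval.

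The documents provide the following follow-up and data:

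- **Stopping treatment.** Section 4.5 states that "pembrolizumab administration will continue until one of the following conditions is observed", and disease progression (4.5.1) is the first condition listed.
- **Safety visit** (section 5.0, footnote f). It takes place "approximately 30 days after the last dose of trial treatment or before the initiation of a new anti-cancer treatment, whichever comes first".
- **Later follow-up** (section 5.0, footnote g). It takes place "24 months after the first treatment of the study regimen for patients who were taken off study treatment for reasons other than disease progression". The item that the flow chart lists for it is "Disease Progression Status". The chart has no vital-status row.
- **Data list** (section 10.1). It includes "date and type of chemotherapy and/or hormonal therapy for metastatic disease" and the date and site of distant metastases at progression. It does not include date of death or date last known alive.
- **Serious adverse events** (section 7.6.1). "Serious adverse events will be captured from the time of the first protocol-specific intervention, until 30 days after the last dose of drug"; later events are reported only if related to study treatment.

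On timing, section 1.0 gives an estimated trial duration of 3 to 4 years. Section 8.0 expects 1 patient per month up to 37, and its precision statement assumes more than 2 years of follow-up for every patient with no dropout.

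**The concern.** A patient who relapses on pembrolizumab stops for progression and so falls outside footnote g. The last scheduled contact is then about a month after the last dose, or earlier if new treatment starts. These are the patients most likely to die. If their OS time is censored at that contact, censoring depends on prognosis, and the Kaplan-Meier estimate rests mainly on patients still free of disease. It would be too high, and its confidence interval would not show it.

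The analysis text does not prevent this. DFS has no written censoring rule that OS could borrow; the nearest text only acknowledges that time to relapse may be right-censored.

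What is at stake is the OS estimate. Two-year DFS is not affected, because relapse is already the event, and OS does not appear among the objectives in section 2.0.

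**Working it through.** **1. Is there another source of survival data?**

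- *Month-24 contact.* It covers patients who stopped for other reasons, including any who relapse later. Patients who stopped for progression are left out.
- *Section 10.1.* Entry excludes a patient who "Has proven or suspected distant metastasis that involves occurrence of breast cancer outside of loco-regional breast and lymph nodes area", so the item on therapy for metastatic disease must refer to treatment after relapse. Some post-relapse information is therefore expected, but no survival date.
- *Safety reporting.* The 7.6.1 window closes 30 days after the last dose unless the event is related. Section 7.6.3 runs to 90 days (30 if new therapy starts), but leaves out deaths from progression of the study cancer.
- *Section 4.6.1.2.* The loss-to-follow-up rule concerns whether tumor response can be judged. It is not an OS rule.

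None of these supplies a date of death for a patient who stopped for progression.

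**2. The plan's own figure.** Section 8.0 gives no figure for OS. Its DFS interval width reproduces: 2 × 1.96 × √(0.8 × 0.2 / 37) = 25.8 points, against a stated width of about 25%.

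**3. Patients concerned.** Relapses by month 24 number about 37 × 0.20 = 7.4 at the planned 80% DFS and 37 × 0.40 = 14.8 at the historical 60%. Those who stop for progression lose scheduled contact.

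**4. Size of the bias (illustrative).** Assumptions, none of them in the documents: exponential times; no death without relapse; median survival after relapse of 12, 24 or 36 months; a share p of relapsers whose contact ends c months after relapse, with the rest seen to month 24.

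- Relapse hazard λ = −ln(S24)/24; death hazard after relapse μ = ln 2 / median.
- Dead by month 24 = ∫₀²⁴ λ e^(−λu) [1 − e^(−μ(24−u))] du.
- Kaplan-Meier limit = exp{−∫₀²⁴ μ R(t)/[D(t)+R(t)] dt}, where D is the proportion disease-free and R the proportion relapsed, alive and still in contact.

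Each cell gives results for medians of 12 / 24 / 36 months:

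| | 2-year DFS 80% | 2-year DFS 60% |
|---|---|---|
| True 2-year OS | 0.906 / 0.942 / 0.959 | 0.804 / 0.880 / 0.914 |
| Deaths among 37 | 3.5 / 2.1 / 1.5 | 7.2 / 4.4 / 3.2 |
| Kaplan-Meier OS, c = 1, p = 1 | 0.988 / 0.994 / 0.996 | 0.973 / 0.986 / 0.991 |
| Bias in points, c = 1, p = 1 | 8.2 / 5.1 / 3.7 | 16.8 / 10.6 / 7.7 |
| Bias, c = 1, p = 0.75 | 6.0 / 3.7 / 2.7 | 11.6 / 7.3 / 5.3 |
| Bias, c = 1, p = 0.5 | 3.9 / 2.4 / 1.7 | 7.2 / 4.5 / 3.2 |
| Bias, c = 6, p = 1 | 4.0 / 2.8 / 2.1 | 7.7 / 5.4 / 4.1 |
| Bias, c = 12, p = 1 | 1.4 / 1.1 / 0.8 | 2.6 / 2.0 / 1.6 |
| 95% CI half-width for OS | 9.4 / 7.5 / 6.4 | 12.8 / 10.5 / 9.0 |

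The half-width is 1.96 × √(S(1−S)/37) at the true OS. A simulation of 400,000 patients (c = 1, p = 1, median 12 months) agreed: Kaplan-Meier 0.988 against a true 0.905 at 80% DFS, and 0.972 against 0.804 at 60%.

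**5. Trial duration.** At 1 patient per month the 37th enters at month 36 or 37, and 24 months of follow-up brings the end to month 60 or 61. Finishing in 48 months would need 36/24 = 1.50 to 37/24 = 1.54 patients per month; finishing in 36 months would need 36/12 = 3.0 to 37/12 = 3.1. A data cut at 48 months under the stated accrual leaves 24 or 25 of 37 patients with 24 months of potential follow-up. The Greenwood interval for 80% DFS then widens from 25.8 to between 27.3 and 27.6 points, a loss of about 1.5 to 1.8 points.

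**The case against.** The strongest objection concerns weight. OS is one sentence, with no hypothesis, target or decision rule, and the monitoring rule does not use it. The largest bias figures need every relapser to be lost one month after relapse, whereas those who relapse after stopping for another reason do get the month-24 contact. At 80% DFS even that extreme stays within the sampling half-width (8.2 against 9.4 points, 5.1 against 7.5, 3.7 against 6.4). This is a single-center trial that expects to record treatment after relapse, so vital status from the chart is not ruled out. The primary endpoint is itself described as being alive with disease control, so the month-24 check must in practice establish whether the patient is alive.

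Most of this stands as a limit on size and importance. It does not close the gap. The month-24 check still omits the patients who stopped for progression, and data that might be found in a chart are neither listed nor tied to a censoring rule. At 60% DFS the extreme case exceeds sampling error at a 12-month median (16.8 against 12.8 points).

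On duration, section 1.0 also gives a participation figure of 3 without a unit. If that means years, the mismatch with 3 to 4 years becomes larger. Duration is in any case a separate and smaller matter.

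**Conclusion.** The concern holds. The plan commits to an OS analysis, its schedule drops the patients most likely to die, and no passage supplies their survival dates or says how to censor them. Censoring at last scheduled contact would bias 2-year OS upward. The documents do not say that this will be done, but they offer no other source of data.

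The direction is firm; the size is not. Over medians of 12 to 36 months after relapse, the overstatement runs from about 1 point at 80% DFS (12 months of contact) to about 17 points at 60% DFS (all relapsers lost after one month, 12-month median). If half the relapsers are lost after one month, it is about 2 to 4 points at 80% DFS and 3 to 7 at 60%.

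This should be fixed, but it does not threaten the primary result. The stated duration of 3 to 4 years is also inconsistent with the plan's own accrual and follow-up, with little effect on DFS precision.

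**What to change.** - **Section 5.0.** Extend the footnote g contact, at about 24 months from first dose, to every treated patient, including those who stopped for progression. A visit, telephone call or chart check would do. Add a vital-status row.
- **Section 10.1.** Add vital status with date of death or date last known alive.
- **Section 8.0.** State that OS is censored at the date last known alive, not at relapse. If vital status will not be collected, do not report OS as an estimate.
- **Section 1.0.** Restate the duration as about 5 years, or state the accrual rate that the shorter period would need (about 1.5 per month for 48 months). Give the unit for duration of participation and make the two figures agree.
- **Wording.** Reconcile section 4.5.6, which takes patients off study when pembrolizumab is completed, with footnotes g and h.

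The cost is one brief contact or chart check per patient, one or two data fields, one sentence on censoring and a longer stated duration. The sample size, the treatment and the primary analysis do not change.
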